In a recent further innovation, intermittent theta burst (iTBS) rTMS has been shown to be as efficacious as 10 Hz rTMS in remediating depression (Garrett-Mayer, 2006). Notably, a single session of excitatory iTBS rTMS entails 600 pulses in merely 3 minutes. More specifically, pulses are delivered in triplets at 50 Hz for 2 s (i.e., 5 Hz triplets) and repeated every 10 s for a total of 190 s (600 pulses). While the use of iTBS in accelerated protocols is only now emerging for the remediation of neuropsychiatric dysfunction, accumulating safety and efficacy results are promising, even among the most impaired and vulnerable patients (Lasonos et al., 2011). From a practical standpoint, theta burst sessions are typically spaced by 20-60 minutes apart with no requirements on the intervening time period. As such, veterans could potentially undergo multiple 3-minute sessions in a single day with more limited interference to daily demands than more conventional 10 Hz protocols.

In substance use disorders, there is mounting evidence that there is an imbalance of neural activity between the executive control network and the reward network. As the executive control network is thought to have a modulatory effect on the reward network (Kober et al., 2010), this imbalance may play a key role in the inability of those with substance use disorders to modulate drug craving and use (Kober et al., 2010; [name] et al., 2015; Sutherland et al., 2012; Volkow et al., 2010; Charboneau et al., 2013; Cousijn et al., 2013). If in fact an imbalance of these two networks results in craving, then it would follow that either the application of excitatory rTMS to the executive control network or inhibitory rTMS to the reward network would result in decreased craving. More than 20 studies have confirmed this relationship [see reviews: Bellamoli et al., 2014; Gorelick et al., 2014; Wing et al., 2013; Barr et al., 2011]. The majority of these studies applied single sessions of excitatory stimulation to the DLPFC with the idea that this type of stimulation can result in enhanced executive control modulation of the reward network and less reactivity to drug cues. Of note, another study demonstrated that inhibitory rTMS applied to the DLPFC resulted in increased craving (Li et al., 2013), providing further evidence of this relationship.

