rTMS. Furthermore, it is well known that in order to derive a meaningful clinical effect, the application of multiple sessions of rTMS are needed. 2: This will be the first trial testing an accelerated rTMS treatment paradigm using established rTMS doses in an addictions population. This is important as there is a clear dose response effect in rTMS, where larger doses of rTMS result in a larger clinical effect ([name] et al., 2010; McDonald et al., 2011). It is additionally important as OUD and other substance use disordered populations may be difficult to treat using the standard treatment paradigm of one session per day over several weeks. 3: This trial will be the first to use rTMS as an adjunct to standard of care opioid treatment. OUD patients, including Veterans, are difficult to engage in outpatient care. Subsequently, a treatment that encourages retention and integration early in the recovery process could have a significant impact on patient outcomes.

RESEARCH DESIGN AND METHODS

Approach Overview (Figure 3): Participants will be recruited from the Ralph H. Johnson VAMC, local VA clinics, and Charleston Center. We will collect data at one week, four weeks, and three months following rTMS completion.

[figure not shown]
Acute Phase: We will screen, consent, enroll, and assess participants during an enrollment session. Following enrollment, each participant will complete baseline measurements of opioid use, opioid craving, pain, and functioning (as outlined below). Following the enrollment session, each participant will be randomized and begin the acute treatment phase of the trial. *Participants will receive a total of six sessions of rTMS on three days during the acute phase of the study over a period of up to three weeks. A period of up to one-week in between treatment days will be allowed to maximize feasibility of intervention deliverability in this population while minimizing risk of a treatment gap that is too long to allow for a summation of effect.* On the third treatment day, pain assessments will be repeated. Craving and pain will be assessed using validated questionnaires.

Continuation Phase: Participants will return at one week, four weeks, and three months for follow-up visits to preliminarily assess the intervention's impact on opioid use, pain, and functional outcomes.

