rTMS Treatments: rTMS will be delivered via a MagPro double blinded rTMS Research System (MagVenture, Denmark) with a Cool-B65 Butterfly Coil (a combined active and sham coil). We will use a standard resting motor threshold (rMT) determination to determine the TMS dose ([name] et al., 2006). Treatment will be delivered at 120% rMT. Each active rTMS treatment will consist of a total of 600 pulses of 50 Hz triplets for 2s, and repeated every 10s for a total of 190s of stimulation. Treatments will be delivered at the EEG coordinate for F3 (approximating the left DLPFC), and will be found using the Beam-F3 method (Beam et al., 2009). This is a treatment paradigm that has been used extensively in other trials ([name] et al., 2008; Short et al., 2011; [name] et al., 2014; Li et al., 2013). Sham sessions will be delivered using an electronic sham system consisting of a coil that mimics the appearance and sound of TMS, combined with a TENS device which produces a small electric shock mimicking the feeling of real rTMS. This type of sham has been demonstrated to be indistinguishable from real rTMS, has been well tolerated ([name] et al., 2010; [name] et al., 2014) and successfully used in other clinical trials ([name] et al., 2008; Arana et al., 2008). During each session of rTMS we will present a series of opioid related images, including those utilized in previous studies (Garland et al., 2015; Garland & Howard, 2014). The application of drug cues during rTMS appears to enhance its efficacy (Dinur-Klein et al., 2014). Opiate craving and stress will be assessed before and after each TMS treatment.

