Statistical Analysis: *Study feasibility will be primarily measured by a) the total number of rTMS sessions completed (out of 18 total sessions) b) the proportion of participants completing all of the rTMS session and c) the proportion of participants completing all of the rTMS sessions as well as the follow-up visits. Study tolerability will be measured as the total number of treatment emergent adverse events. Group differences (active rTMS vs. sham rTMS) in the feasibility and tolerability measures will be estimated using generalized linear models with appropriate distributions (Negative binomial for session and AE count and logit for study treatment completion). In addition to study feasibility, efficacy measures (opioid use amounts, pain, and sleep quality) will be estimated for the entire cohort as well as estimates of between group differences. Changes in study efficacy outcomes from baseline to follow-up visits will be estimated and analyzed using appropriate statistical approaches. When parametric modeling assumptions can be made, changes over time and associated variability will be estimated between treatment groups using general linear mixed models (GLMMs). The GLMMs will allow us to estimate group-specific changes over time and overall effect sizes, along with the variation in those measures, while controlling for relevant baseline covariates (e.g. baseline craving, morphine equivalents, withdrawal). Although we will likely not be powered to detect between-group differences in binary outcomes (i.e. any drug use), such effects will be explored using generalized mixed models, and for time-to-event data (e.g. days to first opioid use), survival analysis models will be constructed. When parametric modeling assumptions do not appear to be valid, alternative (e.g. non-parametric) approaches will be used. Efficacy outcomes will also be analyzed for evidence of differential treatment effects in subgroups determined by gender, race, and ethnicity. Post-hoc exploratory analyses using GLMMs within the active rTMS group will address whether specific characteristics (e.g. demographics, baseline craving, morphine equivalents, withdrawal, PTSD) are associated with a differential treatment effect. The subgroup-specific treatment effects and corresponding confidence intervals will be constructed and will be interpreted in terms of their clinical, rather than statistical, significance, and effect size of treatment to inform future trials will be estimated.* **Missing Data and Attrition:** *Missing data in longitudinal studies can be a problematic feature but can be mitigated through study design considerations. We will make every effort to prevent attrition, e.g., telephone/text/e-mail reminders prior to visits, and reinforcing attendance at each visit. However, these methods do not ensure that all data will be collected, and appropriate analysis methods will be employed to accommodate missing data. Maximum likelihood estimation yields valid inferences assuming ignorable attrition (i.e., attrition is accounted for by covariates or the dependent variable measured prior to dropout). In addition, in keeping with the ITT, we will make every effort to continue assessments for the entire course of randomized treatment, even among those who stop participating in the study assigned intervention or fail to complete the full rTMS time course.*

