c. Potential Risks and Risk Mitigation Strategies:

Potential risks of rTMS: The use of high frequency rTMS has been FDA approved for the treatment of major depressive disorder since 2008. Our stimulation parameters (3000 pulses, 10Hz, 5-Seconds on 10-Seconds off) are nearly identical to the FDA approved protocol (3000 pulses, 10Hz, 4-Seconds On, 8-Seconds off), and have been used safely in many investigations including those in depression, pain, and addictions. We chose to use the slightly longer train duration of 5-seconds rather than 4-seconds due to its safety and efficacy in many trials including our preliminary single session trial with opioid users.

The common clinical dose of rTMS in depression is 36 treatments with 3000 pulses per treatment, for a total of 108,000 pulses. We will deliver a total of 18 treatments over 5 days with 3,000 pulses per treatment, for a total of 54,000 pulses. We subsequently will be giving a substantially lower total dose to each participant than is commonly given to patients being treated for depression. Accelerated treatment paradigms (including those with 6 treatments delivered daily) have been safely delivered in both depression and addictions populations without any clear adverse effect.

Risk of Seizure: The most serious risk associated with the use of rTMS is seizure. Since the adoption and widespread use of standard safety guidelines in 1997, there has only been one documented seizure. The risk of seizure has been estimated to be less than 0.1% which is lower than the risk of seizure associated with pharmacologic antidepressants. The risk of seizure is related to the various stimulation parameters (intensity,frequency, train duration), location of application, pre-existing risk of seizure, and substance/medication factors. In the very rare event a seizure is caused, removing the coil is typically sufficient to stop the seizure, and there is no increased risk of subsequent seizure. In order to mitigate the risk of seizure we will carefully individualize the intensity of stimulus (by performing a resting motor threshold determination), treat using standard treatment protocols (used safely in other studies), and exclude potential participants at higher risk of seizure (those with a past history of seizures, those in withdrawal from alcohol or benzodiazepines, etc).

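### The plan gives conflicting rTMS regimens: six sessions in the design section, 18 in the primary feasibility measure, and a risk section written for a 10 Hz course instead of theta burst

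*Combined protocol and SAP*

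**What the plan says.** Five places in the combined protocol and SAP bear on the regimen.

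- **Research Design and Methods, Acute Phase:** "Participants will receive a total of six sessions of rTMS on three days during the acute phase of the study". The three treatment days may be spread over up to three weeks.
- **rTMS Treatments:** "Each active rTMS treatment will consist of a total of 600 pulses of 50 Hz triplets for 2s, and repeated every 10s", for 190 s in all. Background and Significance describes the same pattern as intermittent theta burst (iTBS): "pulses are delivered in triplets at 50 Hz for 2 s (i.e., 5 Hz triplets) and repeated every 10 s".
- **Statistical Analysis:** feasibility measure (a) is "the total number of rTMS sessions completed (out of 18 total sessions"). Measures (b) and (c) are the proportions completing all sessions, and all sessions plus follow-up. Neither gives a number.
- **Protection of Human Subjects, 1c, Potential risks of rTMS:** "Our stimulation parameters (3000 pulses, 10Hz, 5-Seconds on 10-Seconds off) are nearly identical to the FDA approved protocol", and "We will deliver a total of 18 treatments over 5 days with 3,000 pulses per treatment, for a total of 54,000 pulses". The comparator is "The common clinical dose of rTMS in depression is 36 treatments with 3000 pulses per treatment, for a total of 108,000 pulses".
- **Quantitative Sensory Testing:** testing is scheduled on treatment Days 1 and 3, which fits three treatment days and not five.

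**The concern.** There are two separate conflicts.

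**Session count.** Feasibility is the primary question, and the document does not settle whether 6 or 18 sessions are to be delivered. The figure of 18 is the benchmark for measure (a). Measures (b) and (c) inherit whichever schedule staff believe is in force. The sections that could help do not decide the matter. The 18 sessions over three days in Preliminary Data belong to an earlier trial, and the remark in 1c about six treatments daily concerns other paradigms. Design Considerations says only that there are multiple sessions per day, which fits two or six.

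**Risk section.** Whichever count is right, 1c defends a regimen that differs from the delivered one in frequency, pattern, pulses per session, train length and number of days. The same section states that "The risk of seizure is related to the various stimulation parameters" and lists frequency among them. Its claim of near-identity with the approved 10 Hz protocol therefore does not carry over to 50 Hz triplets. Background says accelerated use of iTBS is only beginning to appear and cites promising safety results. The risk section uses neither those results nor those parameters.

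Staff, analyst and safety reviewer could each work from a different regimen while following the same document.

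**Working it through.** **Inputs.** Six sessions on three days (Acute Phase); 18 sessions (Statistical Analysis); 600 pulses per session in 2 s trains every 10 s, 190 s (rTMS Treatments); 5 triplets per second (Background); 18 treatments over 5 days, 3,000 pulses, 10 Hz, 5 s on and 10 s off, comparator 36 × 3,000 (section 1c); n = 20 (Sample Size Justification).

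**Step 1: reproduce the plan's figures.**
- Risk section: 18 × 3,000 = 54,000 and 36 × 3,000 = 108,000. Both match, so 1c describes a coherent but different regimen and is not a single typing slip.
- Theta burst: 5 triplets/s × 3 pulses × 2 s = 30 pulses per train; 600 / 30 = 20 trains; 19 × 10 s + 2 s = 192 s. This agrees with the stated 600 pulses and 190 s.

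**Step 2: session count.**
- Literal reading: 6 / 3 = 2 sessions per day. Six-per-day reading: 6 × 3 = 18.
- Full adherence read against 18: 6/18 = 33% under the literal reading, 18/18 = 100% under the other.
- Scheduled sessions in the trial: 20 × 6 = 120, or 20 × 18 = 360.

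**Step 3: total dose per participant.**

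| Regimen | Pulses | 54,000 relative to it | Share of the 108,000-pulse course |
|---|---|---|---|
| 6 sessions × 600 | 3,600 | 15-fold | 3.3% |
| 18 sessions × 600 | 10,800 | 5-fold | 10% |
| Risk section, 18 × 3,000 | 54,000 | 1 | 50% |

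**Step 4: a single session, as delivered and as justified.**

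| | rTMS Treatments | Risk section 1c |
|---|---|---|
| Pulse rate | 50 Hz within triplets; 30 / 2 s = 15 pulses/s averaged over the train | 10 Hz |
| Pulses per train | 30 | 10 × 5 = 50 |
| Trains | 20 | 3,000 / 50 = 60 |
| Duration | about 190 s | 59 × 15 s + 5 s = 890 s, about 14.8 min |

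**Step 5: daily burden.** Assume gaps of 20 to 60 minutes, which Background calls typical for theta burst; the plan fixes no spacing for this trial.
- Two sessions a day: 2 × 190 s = 6.3 min of stimulation plus one gap, about 26 to 66 minutes.
- Six sessions a day: 6 × 190 s = 19 min plus five gaps, about 119 to 319 minutes, or 2 to 5.3 hours.

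**The case against.** The best reply on the count is that 18 was probably meant. Two of the three statements of this trial's count give 18 (Statistical Analysis and section 1c), and six sessions on each of three days gives exactly 18. The plan to ramp up intensity over the first three sessions also fits a long course better, since it would take up half of a six-session course. This has some weight and makes a dropped per-day qualifier in the Acute Phase paragraph plausible. It is not decisive. That paragraph gives six as the total, and the supporting count in 1c sits in a sentence whose days and pulse number do not match this trial.

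The reply on statistics is that little turns on the figure. Measure (a) is a count, no success threshold or progression rule is attached to it, and the active-sham comparison of counts does not use 18. All of that is correct. The 33% arises only if six sessions are delivered and adherence is then read against 18. What remains is that the reported level of adherence, as distinct from the group contrast, has no settled denominator.

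The reply on safety is that the risk section overstates exposure: delivered trains are shorter (2 s against 5 s) and total pulses far fewer. Motor-threshold dosing, seizure-risk exclusions and the monitoring board do not depend on the 10 Hz text, and Background cites iTBS safety work. This stands, and no added risk is shown. It does not make the 1c argument apply to the pattern being delivered.

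**Conclusion.** The concern holds, and the text must be corrected. It is a contradiction between stated figures, not missing detail. The primary feasibility benchmark is 18 where the design section gives six in total, a threefold difference. The documents do not settle which is intended, although 18 has some support. Reading the design as six per day would repair the count only. The risk section would still give the wrong frequency, pattern, pulse number, train length and days, with total dose overstated 5-fold (18 sessions) or 15-fold (six sessions).

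The pulse totals rest on 600 pulses per session, as the rTMS Treatments section states. The between-arm comparison of session counts and the sample size are unaffected, and no excess dose is claimed. The damage is to how adherence will be reported, to the definition of completing all sessions, and to a safety justification that does not describe the treatment.

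**What to change.** State one regimen (sessions per day, number of treatment days, pulses per session, pattern) and use it throughout.

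1. **Acute Phase.** If six per day is intended, write six sessions on each of three days, 18 in total. If six in total is intended, keep the figure and add two per day, if that is the split.
2. **Statistical Analysis.** Set the denominator in (a) to the scheduled number, 18 or 6, and give the same number for all sessions in (b) and (c).
3. **Section 1c.** Replace the 10 Hz parameters, the 5-day schedule and the 54,000-pulse comparison with the theta-burst parameters. The total becomes 10,800 or 3,600 pulses. Bring in the accelerated-iTBS safety evidence that Background already cites.
4. **Consistency check.** Table 1 has a column for TMS Sessions 1-3, apparently meaning treatment days. The site-discomfort paragraph ramps intensity over the first three sessions. Both should use the term session in the same sense as the rest of the plan.

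The cost is a wording amendment to the design, analysis and risk sections. It needs no extra participants, visits or procedures, and the sample size does not change.

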Risk of Site discomfort and headache: Two relatively common risks associated with the use of rTMS include the risk of mild transient site discomfort during treatment (most patients), and the risk of headache (Approximately 5%) following treatment. Both of these potential side effects are typically mild. In terms of mitigating site discomfort, we will slowly ramp up stimulation intensity during the first three sessions. In our experience both clinically and experimentally this is a successful strategy. Additionally, due to the anti-pain effect of rTMS, participants rapidly adjust to stimulation. In the unusual circumstance that a headache is

caused by rTMS, over the counter analgesics are sufficient to alleviate the headaches, and will be available to patients on the inpatient unit.

Potential hearing loss: The discharge of the rTMS coil generates a high-energy click that may cause cochlear damage. Humans exposed to rTMS have shown temporary increases in auditory threshold (especially at high frequencies) lasting at least 5 minutes and less than 4 hours. Foam earplugs can protect against these changes and will be worn during rTMS sessions.

Safety in the case of pregnancy: This protocol will exclude pregnant women. Pregnancy status will be confirmed as part of the standard screening process.

Pain task: The pain task may cause discomfort but will not cause injury. The task will be stopped when it becomes painful to the participant.

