5. DATA AND SAFETY MONITORING PLAN

a. Summary of the Protocol.

This application proposes to investigate feasibility and acceptability of rTMS in opioid use disordered Veterans with chronic pain. Inclusion/exclusion criteria are outlined above.

b. Trial Management.

The study will be managed from Ralph H. Johnson VA Medical Center. The target population is described above in the inclusion/exclusion criteria.

c. Data Management and Analysis.

Data will be entered by research assistants directly into a computer using standard database software using REDCap. The data analysis plan is outlined in the Data Analysis Plan section.

d. Quality Assurance.

Quarterly data audits will be conducted. Confidentiality protections are outlined above.

e. Regulatory Issues.

Potential conflicts of interest will be reported using the VA rules for disclosure. Adverse Events (AEs)/Serious Adverse Events (SAEs) occurring during the course of the project will be collected, documented, and reported in accordance with protocol and IRB reporting requirements. All research staff involved with adverse event reporting will receive general and protocol specific AE/SAE training including identification, assessment and evaluation, and documentation and reporting. A research specialist will identify any potential adverse events during the course of the study from participant self-report and administration of the visit assessments and procedures. The research assistant will provide information to a study physician, who will be responsible for AE/SAE assessment and evaluation including a determination of seriousness and study relatedness. Any significant actions taken by the local IRB and protocol changes will be relayed to VA RR&D.

f. Definition of AE and SAE.

An Adverse Event (AE) is defined as any untoward medical occurrence in a study subject administered a pharmaceutical product that does not necessarily have a causal relationship with this treatment (ICH GCP). Any unwanted change, physically, psychologically or behaviorally, that occurs in a study participant during the

course of the trial is an adverse event. A Serious Adverse Event (SAE) is defined as an adverse event that has one of the following outcomes:

- Results in death,
- Is life-threatening,
- Requires inpatient hospitalization or prolongation of existing hospitalization,
- Results in persistent or significant disability/incapacity,
- Is a congenital anomaly/birth defect OR

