- Requires intervention to prevent one of the above outcomes.

g. Documentation and Reporting.

AEs/SAEs are documented and reported as per protocol and IRB requirements. Research staff will identify adverse events and obtain all available information to assess severity, seriousness, study relatedness, expectedness, outcome and the need for change or discontinuation in the study intervention. Adverse events are generally documented on AE Logs and AE Case Report Forms (CRFs). Additional relevant AE information if available should be documented in a progress note in the research record as appropriate to allow monitoring and evaluating of the AE. If the AE meets the definition for serious, appropriate SAE protocol specific reporting forms are completed and disseminated to the appropriate persons and within the designated timeframes as indicated above. For each AE/SAE recorded, the research staff will follow the AE/SAE until resolution, stabilization or until the participant is no longer in the study as stated in the protocol. When a reportable SAE is identified, the research staff will notify the MUSC Institutional Review Board (IRB) and VA R&D within 24 hours and complete the AE report form in conjunction with the PI. The MUSC IRB meets monthly and is located at [name]. The MUSC IRB has a MOU to provide HHRP oversight for clinical research conducted at the Ralph H. Johnson VA Medical Center. Communication with the IRB is through email, memos, official IRB forms, and online reporting. A report will also be sent to the VA RR&D program officer assigned to the project.

If complete information is not available when the initial 24-hour SAE report is disseminated, follow-up information will be gathered to enable a complete assessment and outcome of the event. This information may include hospital discharge records, autopsy reports, clinic records, etc. The research staff will attach copies of source documents to the SAE report for review by the PI and for forwarding to the NIH program officer as appropriate within 2 weeks of the initial SAE report. In addition, the PI will provide a signed, dated SAE summary report, which will be sent to the VA RR&D Project Officer within two weeks of the initial SAE report.

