We will report adverse events to the Medical University of South Carolina (MUSC) Institutional Review Board (IRB) online as soon as possible, but no later than 10 working days after the investigator first learns of the event. The MUSC IRB AE reporting requirements are as follows: All deaths that occur during the study or 30 days post termination from the study are required to be reported as adverse events even if they are expected or unrelated. Other adverse events are reportable to the MUSC IRB if the AE is unexpected AND related or possibly related AND serious or more prevalent than expected. All three criteria must be met for an AE to be reported to the MUSC IRB. The IRB definition of unexpected is that the AE is not identified in nature, severity or frequency in the current protocol, informed consent, investigator brochure or with other current risk information. The definition of related is that there is a reasonable possibility that the adverse event may have been caused by the drug, device or intervention. Reportable AEs are reviewed by the IRB Chair and reported to the IRB Board at the next meeting.

h. Trial Safety.

The potential risks and benefits and methods to minimize these risks are outlined above. The research staff will report any unexpected AEs or any scores of "severe" on the side-effect symptom rating form or any FDA-defined serious AEs to the PI within 24 hrs so that the PI can decide on the appropriate action. All unexpected AEs will be monitored while they are active to determine if treatment is needed. Study procedures will follow the FDA's Good Clinical Practice Guidelines (www.fda.gov/oc/gcp). Any outside requests for information or any breaches in confidentiality will be reported to [name].

An interim analysis is not planned at this time.

i. DSM Plan Administration.

[name] will be responsible for monitoring the study, and will participate in weekly study meetings. A DSM report will be filed with the IRB and VA R&D on a yearly basis, unless greater than expected problems occur. The report will include participant characteristics, retention and disposition of study participants, quality assurance issues and reports of AEs, significant/unexpected AEs and serious AEs. We will report outcomes at the end of the trial.

j. DSM Board

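### The only named tolerability measure is an unweighted adverse event count, which can dilute a small excess of related moderate or severe events

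*Combined protocol and SAP*

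**What the plan says.** The Statistical Analysis section names one tolerability measure: "Study tolerability will be measured as the total number of treatment emergent adverse events". Active and sham are compared with generalized linear models, specified as "Negative binomial for session and AE count and logit for study treatment completion". The section gives no split by severity, seriousness or relatedness, no rule for repeated symptoms and no level that would count as tolerable.

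Other sections determine what enters the count:

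- **Definition (section 5.f).** No causal link to treatment is needed. "Any unwanted change, physically, psychologically or behaviorally, that occurs in a study participant during the" course of the trial is an adverse event.
- **Expected effects (section 1.c).** The common ones are "mild transient site discomfort during treatment (most patients" and "the risk of headache (Approximately 5%) following treatment". Both are described as typically mild.
- **Sham (rTMS Treatments).** The sham coil is "combined with a TENS device which produces a small electric shock mimicking the feeling of real rTMS".
- **What is recorded (section 5.g).** Staff are to "obtain all available information to assess severity, seriousness, study relatedness, expectedness", outcome, and whether the intervention needs to be changed or discontinued. Section 5.h escalates severe scores "on the side-effect symptom rating form" to the principal investigator.
- **Schedule (Table 1).** An adverse events row, marked at the TMS sessions, has rTMS tolerability as its stated purpose.

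The severity, relatedness and discontinuation information serves safety reporting. Nothing in the Statistical Analysis section brings it into the tolerability measure.

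**The concern.** An unweighted count gives a transient scalp sensation and a serious related event the same weight. If mild sensations are logged in both arms, because the sham is built to produce them, they add a shared background that pulls the count ratio toward 1. A few related moderate or severe events in the active arm could then barely move the reported result.

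The broad definition adds a second difficulty. Worsening pain or opioid use can qualify as an unwanted change, yet the Statistical Analysis section already treats pain and opioid use as efficacy outcomes. A difference in efficacy could therefore reappear as a difference in tolerability.

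This matters because the Sample Size Justification says the trial should allow tolerability to be assessed, and that its model-based estimates will inform the larger trial.

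**Working it through.** The plan states no adverse event rate, tolerability threshold or precision target for tolerability, so there is no figure of its own to reproduce. The check asks how large the mild share could be, and what that does to the comparison.

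**Inputs from the documents.** Ten participants per arm (Sample Size Justification). Site discomfort in most patients and headache in about 5% (section 1.c). Six sessions (Acute Phase), or 18 (Statistical Analysis and section 1.c).

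**Assumptions.** Let p be the probability of site discomfort per counting occasion; most patients is taken as 0.51, 0.70 or 0.90. Let S be the number of counting occasions per participant: 1 if a symptom is logged once, 6 or 18 if logged per session. Headache is 0.05 per occasion. Let m be all other adverse events per participant. The documents give no per-session rate for either effect, and none for m.

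**Step 1: share of the count that is site discomfort.** Share = pS / (pS + 0.05S + m).

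With m = 1:

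| p | S = 1 | S = 6 | S = 18 |
|---|---|---|---|
| 0.51 | 33% | 70% | 83% |
| 0.70 | 40% | 76% | 87% |
| 0.90 | 46% | 81% | 90% |

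Example: p = 0.51, S = 6 gives 3.06 / (3.06 + 0.30 + 1) = 70%.

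**Step 2: where discomfort stops being the majority.** The share is 50% when m = (p − 0.05)S.

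- S = 1: m = 0.46 to 0.85 other events per participant.
- S = 6: m = 2.76 to 5.10.
- S = 18: m = 8.28 to 15.30.

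Counting only discomfort and headache (m = 0), discomfort is 0.51/0.56 = 91% to 0.90/0.95 = 95%. That is a share of two selected effects, not of all adverse events.

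**Step 3: dilution.** Take p = 0.70 and three extra severe events in the active arm. For simplicity, discomfort is the only background.

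- Per session, six sessions: 0.70 × 6 × 10 = 42 discomfort events per arm. Ratio = 45/42 = 1.07. The Poisson standard error of the log ratio is √(1/45 + 1/42) = 0.215, giving a 95% interval of about 0.70 to 1.63.
- Once per participant: 0.70 × 10 = 7 per arm. Ratio = 10/7 = 1.43. The standard error is √(1/10 + 1/7) = 0.493, giving about 0.54 to 3.75.

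Overdispersion, which the negative binomial model allows for, would widen both intervals. The same three events raise the count by 7% or 43%, depending only on a counting rule the plan does not state.

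**Step 4: precision of a proportion.** With 0 of 10 participants affected, the two-sided exact 95% upper limit is 1 − 0.025^(1/10) = 30.8%. With 2 of 10 the interval is about 2.5% to 55.6%, and 2/10 against 0/10 gives a Fisher p of about 0.47.

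**The case against.** The strongest reply is that the mild share is inferred. No section says site discomfort will be logged as an adverse event, still less at each session. Section 1.c describes intensity being ramped up over the first three sessions and participants adjusting rapidly, which argues against a constant per-session rate. This stands. A reader might infer that the measure mostly counts site discomfort, but the documents support that only under per-session counting with few other events. The broader the definition, the smaller the discomfort share.

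Second, a reader might infer that the plan cannot show whether the course is tolerable. That goes too far. Sessions completed and full completion are compared by arm and bear on tolerability. Severity, relatedness and need for discontinuation are recorded, severe ratings and serious events reach the principal investigator within 24 hours, and the monitoring board reviews rate and severity. Severe events would not be hidden from safety oversight. However, completion is analysed as feasibility, without reasons for stopping, and Design Considerations notes that these patients often miss appointments, so non-completion cannot be read as intolerance. Safety oversight is also not the tolerability result the trial will report.

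Third, discomfort need not cancel between arms. The documents say the sham mimics the sensation, not that event rates will be equal. Shared events dilute the ratio; they do not remove a difference.

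Fourth, the side-effect form is not named in Table 1, but it may be the instrument behind the adverse events row. Its absence by name does not show that it is unscheduled.

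Finally, this is an exploratory pilot, and binary measures at ten per arm are imprecise. That also stands, and it limits what the fix can deliver.

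**Conclusion.** The concern holds in a limited form. The named tolerability measure is an unweighted count of treatment-emergent adverse events with no severity or relatedness split and no counting rule. Taken alone, its ratio does not show tolerability and can dilute a small excess of related moderate or severe events.

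The size depends on assumptions the documents do not settle: discomfort in 51% to 90% per counting occasion, headache in 5% per occasion, and an unknown rate of other events. Mild discomfort would be a majority under per-session counting over six sessions unless other events exceed about 2.8 to 5.1 per participant. It need not be a majority under once-per-participant counting. This is a worthwhile, inexpensive improvement to the analysis plan and not a defect that prevents the trial from assessing tolerability.

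**What to change.** In the Statistical Analysis section, make these the main tolerability summaries, by arm with exact 95% confidence intervals:

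1. the proportion of participants with at least one possibly related adverse event rated moderate, severe or serious;
2. the proportion stopping rTMS because of an adverse event.

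Also:

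- state whether a repeated symptom counts once per participant or once per session;
- report worsening pain and opioid use separately, since they are already efficacy outcomes;
- keep the total count and its negative binomial comparison as a secondary description;
- reconcile the six-session statement in the Acute Phase text with the 18-session statements in Statistical Analysis and section 1.c, because the number of sessions drives any per-session count.

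The cost is analysis plan wording. Severity, relatedness and need for discontinuation are already to be recorded under section 5.g. The downside is imprecision: even 0 of 10 leaves an upper limit of 30.8%, so the proportions should be read descriptively and not as a test between arms.
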